1.1 RATIONALE FOR THERAPY

Our primary hypothesis is that up to seven sequential 24-hour SCD treatments will improve survival in patients with Acute Kidney Injury (AKI) as compared to CRRT alone (standard of care). Further, SCD therapy will reduce the duration of maintenance dialysis secondary to AKI due to acute tubular necrosis (ATN). ATN is an acute reversible process and if not reversed in three months, it may not be reversed at all. [1, 2] Studies suggest that approximately 10-20% of AKI patients do not recover renal function [3, 4] and, therefore, require chronic dialysis.

Importantly, acute kidney injury is a highly lethal condition in critically ill patients. Despite improvements in acute medical care and advances in dialysis therapies, the mortality rate during the past four decades of this condition has not improved. Critically ill patients with AKI in hospital

ICU settings have mortality rates of up to 50%, including pediatric patients [5, 6, 7, 8, 9, 10, 11, 12]

AKI promotes a systemic inflammatory response syndrome (SIRS) which results in systemic microvascular damage and, if severe, multi-organ dysfunction. [13, 14] Activated circulating leukocytes play a central role in this process. [15] Leukocytes, especially neutrophils, are major contributors to the pathogenesis and progression of many inflammatory disorders, including SIRS, sepsis, ischemia reperfusion injury, and acute respiratory distress syndrome (ARDS). Many therapeutic approaches are under investigation to limit the activation and tissue accumulation of leukocytes at sites of inflammation to minimize tissue destruction and disease progression. [16, 17, 18] Preclinical studies utilizing a porcine model of septic shock have demonstrated that SCD therapy immunomodulates activated circulating leukocytes. This effect is associated with improvement of multiorgan dysfunction. [19]

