2.4 PILOT STUDY USA ARF-002 - IDE [REDACTED]^[22]

2.4.1 STUDY SUMMARY

Acute kidney injury (AKI) is characterized by deterioration in kidney function resulting in multisystem abnormalities. Much of the morbidity and mortality associated with AKI result from a systemic inflammatory response syndrome (SIRS). This study described herein was a prospective, single-arm, multicenter US study designed to evaluate the safety and efficacy of the Selective Cytopheretic Device (SCD) treatment on AKI requiring continuous renal replacement therapy (CRRT) in the ICU. The study enrolled 35 subjects. The mean age was 56.3 ± 15 . With regard to race, 71.4% of the subjects were Caucasian, 22.9% were Black, and 5.7% were Hispanic. Average SOFA score was 11.3 ± 3.6 . Death from any cause at Day 60 was 31.4%. Renal recovery, defined as dialysis independence, was observed in all of the surviving subjects at Day 60. The results of this pilot study indicate the potential for a substantial improvement in patient outcomes over standard of care therapy, which is associated with a greater than 50% 60-day mortality in the literature. The SCD warrants further study in scientifically sound, pivotal trial to demonstrate reasonable assurance of safety and effectiveness.

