2.5 PIVOTAL STUDY (PROTOCOL SCD-003) - IDE [REDACTED]^[23]

2.5.1 STUDY SYNOPSIS

Per the SCD-003 Protocol, our primary hypothesis is that up to seven sequential 24-hour SCD treatments will improve survival in patients with Acute Kidney Injury (AKI) as compared to CRRT alone (standard of care). Further, SCD therapy may reduce the duration of maintenance dialysis secondary to AKI due to acute tubular necrosis (ATN). ATN is an acute reversible process and if not reversed in three months, it may not be reversed at all. [1, 2] Studies suggest that approximately 10% of AKI patients do not recover renal function [3, 4] and, therefore, require chronic dialysis. Importantly, acute kidney injury is a highly lethal condition in critically ill patients. Despite improvements in acute medical care and advances in dialysis therapies, the mortality rate during the past four decades of this condition has not improved. Critically ill patients with AKI in hospital ICU settings have mortality rates of 50 to 80%. [5, 6, 7, 8, 9, 10, 11, 12]

The SCD requires regional citrate anticoagulation be used for the entire CRRT and SCD blood circuits. Per SCD-003, Section 5.1:

Each participating clinical site is to use their regional citrate anticoagulation protocol for the CRRT and SCD-ARF circuits (Study Arm) and for the CRRT only (Control Arm). The recommended ionized calcium level (measured post SCD-ARF) in the CRRT and SCD-ARF blood circuit should be between 0.25 and 0.40 mmol/L.

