60 Day Mortality	CRRT + SCD N= 69	CRRT Alone N= 65	Overall N=134
All Subjects Enrolled	100.0% (69/69)	100.0% (65/65)	100.0% (134/134)
Alive	61% (42/69)	64% (38/59*)	63% (80/128)
Dead	39% (27/69)	36% (21/59*)	38% (48/128)

*Does not include six subjects LTFU (002-003, 011-002, 004-007, 011-004, 013-002, 007-025)

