2.5.3 EFFICACY RESULTS AT INTERIM ANALYSIS

As a result of the mortality in Control Arm (CRRT alone) being approximately 10% lower than published levels of 45-50%, further analysis was undertaken. As a result of the analysis, it was discovered that amount of time the patient was maintained in the recommended ionized calcium range (0.25-0.40 mmol/L per SCD-003 protocol) presented a difference in efficacy outcomes. One reason for the deficiency in clinical trial execution to ensure the protocol's riCa target range of ≤ 0.40 mmol/L be maintained could be attributed to the national shortage of injectable calcium. If the patient did not experience circuit clotting, the PIs emphasis of achieving and continuously maintaining the patient in the recommended ionized calcium range was not consistently adhered to. In addition, the injectable calcium shortage resulted in 9 of the 21 open clinical sites unable to enroll subjects due to low hospital inventories of injectable calcium.

Of the 134 subjects enrolled in the SCD-003 protocol at the time of the interim analysis, 19 SCD subjects (CRRT+SCD) and 31 control subjects (CRRT alone) were maintained in the protocol's recommended range ($(\leq 0.40 \text{ mmol/L}) \geq 90\%$ of the therapy time).

Table 6 details all cause mortality at day 60 (primary endpoint) of the treated subjects which received the recommended ionized calcium (riCa) and **Table 7** details all cause mortality at day 60 of the treated subjects which did not receive the recommended ionized calcium (nriCa).

Table 6: 60 Day Mortality of Subjects – Recommended Ionized Calcium Range (riCa)

60 Day Mortality riCa	CRRT + SCD N= 19	CRRT Alone N= 27*	Overall N=46
Alive	84% (16/19)	59% (16/27)	70% (32/46)
Dead	16% (3/19)	41% (11/27)	30% (14/46)
Pearson chi2(1) = 3.2793 Pr = 0.070			

*Three subjects LTFU (004-007, 007-025, 011-004). One subject withdrew consent (013-002).

Table 7: 60 Day Mortality of Subjects – Non Recommended Ionized Calcium Range

60 Day Mortality nriCa	CRRT + SCD N= 50	CRRT Alone N= 32*	Overall N=82
Alive	52% (26/50)	69% (22/32)	59% (48/82)
Dead	48% (24/50)	31% (10/32)	42% (34/82)
Pearson chi2(1) = 2.2555 Pr = 0.133			

*Two subjects LTFU (002-003, 011-002). Two subjects enrolled to CRRT alone arm (012-002, 003-015) however not treated.

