Besides the test of the hypothesis the study is focused on observable, empirical and laboratory determinations of patient safety while on the SCD. Previous human trials have been conducted on the SCD device and the protocol contains a review of AE and SAE data from all SCD human studies and findings from those studies contributed to constructing the investigative safety profile. Safety endpoint measures specified in the protocol include adverse events, laboratory safety parameters, vital signs, ventilation status and hemodynamic variables. Device integrity and performance measurements are also defined as are circumstances which demand premature termination of SCD treatment.

Prolonged exposure to the SCD is anticipated to result in superior outcomes, although as noted above, this pilot study is not designed to assess for efficacy. However, we understand that a minimum amount of exposure to the SCD will be required for an appropriate safety analysis and for making any inference regarding efficacy. The ppCRRT experience demonstrated that the majority of patients (201/370) received CRRT for 1 to 7 days and exhibited 65% survival (Symons et al CJASN 2007 Table7). Assuming our trial includes patients with similar illness severity, we have established a 72 minimum number of hours a patient will be treated with the SCD to be included in the final outcome analysis.

This trial is an early safety efficacy study but is not powered for statistical significance. Insights into a comparison of historical controls matched to SCD treated patients will utilize the ppCRRT Registry to match for: etiology of AKI, co-morbidities, CRRT modality, dose and form of anticoagulant, adverse events. [10].

The ppCRRT Registry has data fields for the primary reason for CRRT, including AKI and its cause, as well as co-morbidities which will be matched for primary organ system involvement. The CRRT modality was evenly distributed between convective and diffusive modality, with 60% of the convective modalities provided as CVVH and 40% as CVVHDF. The anticoagulant protocol will be standardized with ACD-A/CaCl₂ and all centers used the same protocol in ppCRRT Registry as outlined in this study protocol. Thus, the ppCRRT Registry dataset will be able to be matched to our study patient cohort. Also as noted above, patients will be matched for age, size and PRISM II score.

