The Prospective Pediatric CRRT (ppCRRT) database will be used as a control for the CRRT treatment related factors including: patient age, gender, primary cause of AKI, total treatment duration, CRRT modality (CVVH, CVVHD, CVVHDF), CRRT small solute clearance (ml/1.73m²/hour), baseline estimated GFR (using the original Schwartz formula, which was used in the ppCRRT), urine output in the 24 hours prior to CRRT initiation (ml/kg/hour), percent fluid overload at CRRT initiation based on admission ICU weight, vasoactive medication number at time of CRRT initiation and mean airway pressure at CRRT initiation.

An additional analysis will also evaluate patients who have achieved targeted iCa levels during 90% of treatment time and those who do not.

In summary this protocol meets all criteria necessary for clinical scientific inquiry related to a test of hypothesis in a well monitored environment focused on patient safety during the conduct of the study. Basic statistics will be performed on the data sets along with historical data comparisons and subjected to subset analysis where appropriate. The results will help to guide the design of a future pivotal study of this device.

The rational for therapy, study objectives and endpoints, design, inclusion and exclusion criteria are explicitly defined. Patient safety parameters are well documented including safety reporting, safety observations and assays, procedures for patient withdrawal and study discontinuation criteria along with monitoring device integrity and performance. Lastly, a review of all prior SCD human study safety data is included in the protocol for full disclosure to study investigators and the informed consent document includes a full description of all known and potential risks of the device treatment.

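### The ppCRRT Registry comparison has no matching, adjustment or sensitivity analysis for calendar period, so an era or selection difference could not be told apart from an SCD effect

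*Combined protocol and SAP*

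**What the plan says.** The trial has one arm. Section 3.1 puts the comparison with historic data on mortality and dialysis dependency into the primary objective. Section 10 schedules an efficacy evaluation against historical controls once 16 patients have completed 60 days, while the synopsis allows up to 30 patients.

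Section 11 names the control source: "Insights into a comparison of historical controls matched to SCD treated patients will utilize the ppCRRT Registry to match for" AKI etiology, co-morbidities, CRRT modality, anticoagulant dose and form, and adverse events. It adds that "patients will be matched for age, size and PRISM II score". A later paragraph lists 11 patient and treatment factors to be controlled through the registry, from age and gender to fluid overload and mean airway pressure. Year of treatment appears in none of these lists. The registry is cited from a report dated 2007 in Section 14; the same reference list contains work from 2015.

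On purpose, Section 11 says that the pilot was not designed to judge efficacy and claims no power. It also says "In summary this protocol meets all criteria necessary for clinical scientific inquiry related to a test of hypothesis", and that the results will help to shape a pivotal study.

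Three background statements bear on historical benchmarks:

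- Section 1.1: "the mortality rate during the past four decades of this condition has not improved".
- Section 2.4.1, on the single-arm study ARF-002 (31.4% mortality at day 60): its results are said to suggest that the SCD might offer "a substantial improvement in patient outcomes over standard of care therapy, which is associated with a greater than 50% 60-day mortality in the literature".
- Section 2.5.3, on the randomised study SCD-003: "As a result of the mortality in Control Arm (CRRT alone) being approximately 10% lower than published levels of 45-50" per cent, the sponsor looked more closely at the data.

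**The concern.** Without concurrent controls, the difference between SCD patients and registry patients contains the device effect plus whatever else differs between the two groups. Matching on severity, cause and CRRT factors can absorb part of a change in case mix or practice. It cannot be relied on to absorb improvements in care that the matched variables do not measure, and nothing in the plan would show how much is left.

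The sponsor's own programme shows why this deserves a safeguard. Published rates were a poor guide to control mortality in SCD-003, and an encouraging single-arm result in ARF-002 was followed by a randomised comparison with 39% mortality on SCD and 36% on CRRT alone. Section 11 carries no precaution from that experience into the registry comparison.

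At stake is the reading of the efficacy result. If registry mortality is higher for reasons unrelated to the device, an inert device can look helpful, and that impression would feed the design of a pivotal study in children. Because the historical comparison also sits inside the primary safety objective, a benchmark that is too high would make the observed mortality look more reassuring than it is.

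**Working it through.** **1. The plan's own figure, SCD-003 control mortality (Section 2.5.2, Table 5).**

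- 21/59 = 35.6%.
- Gap to the published 45–50% (Section 2.5.3): 45 − 35.6 = 9.4 points; 50 − 35.6 = 14.4 points. The protocol's description of about 10% lower is consistent with this.
- Exact (Clopper-Pearson) 95% CI for 21/59: 23.6% to 49.1%. It includes 45% and excludes 50%.
- The footnote to Table 5 says of the control arm: "Does not include six subjects LTFU". With all six counted alive, 21/65 = 32.3%; with all six counted dead, 27/65 = 41.5%. The gap to 45–50% then runs from 12.7–17.7 points to 3.5–8.5 points.
- Published rates are themselves unsettled in the protocol. Section 2.5.1 has: "Critically ill patients with AKI in hospital ICU settings have mortality rates of 50 to 80" per cent. Against that range the gap would be 14 to 44 points.

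So SCD-003 shows that a literature benchmark can miss actual control mortality. It does not measure a time trend.

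**2. The registry's own figure (Section 11).** Survival of 65% is quoted for the 201 of 370 registry patients on CRRT for 1 to 7 days, so mortality is 100 − 65 = 35%. This is 35.6 − 35 = 0.6 points from the SCD-003 control arm. It is a subgroup; overall registry mortality is not given.

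**3. What drift would do: illustration.** Assumptions:

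- The device is inert.
- The benchmark is fixed at 35%, with no sampling error of its own.
- Drift d is a fall in mortality since the registry period that matching does not remove, so SCD patients die at p = 0.35 − d.

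An apparent benefit of 10 points or more means observed mortality of 25% or less: at most k = 4 deaths of 16 (0.25 × 16 = 4), or k = 7 of 30 (0.25 × 30 = 7.5, rounded down).

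P(X ≤ k) = Σ from x = 0 to k of C(n, x) pˣ (1 − p)ⁿ⁻ˣ

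| Assumed drift | p | n = 16, k = 4 | n = 30, k = 7 |
|---|---|---|---|
| 0 | 0.350 | 29% | 12% |
| 5 points | 0.300 | 45% | 28% |
| 9.4 points | 0.256 | 61% | 48% |

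The first row is sampling noise alone. The part due to drift is the increase over that row: at n=16, 45 − 29 = 16 points and 61 − 29 = 32 points; at n=30, 28 − 12 = 16 points and 48 − 12 = 36 points. The larger sample reduces the noise but does not protect against drift. The 9.4 is borrowed from step 1 only as a plausible size.

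**The case against.** The strongest reply is that the plan claims little. Section 11 presents the comparison as a source of insight, disclaims power and an efficacy design, and plans only basic statistics. It specifies no significance test. The matching variables include severity, fluid overload, vasoactive support and CRRT dose, which can absorb some change in case mix and practice. Registry enrolment dates are not given, so a gap in time is inferred from citation years. All of this is fair and lowers the weight of the point. It does not supply the missing safeguard, because an efficacy evaluation is still scheduled and is meant to inform a pivotal study.

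Several stronger readings are tempting, and the documents do not support them.

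- *That the 9 to 14 points in SCD-003 is an era effect that would be credited to the SCD.* It compares one trial arm with literature rates, not an earlier with a later period. Eligibility, case mix, loss to follow-up and chance could explain it. SCD-003 is not described as pediatric, and its comparator was not this registry.
- *That an inert device would probably look beneficial.* If the benchmark were 45–50% and true mortality 21/59, an apparent benefit of 10 points or more would have probability 47–67% at n=16 and 48–76% at n=30. Nothing shows that matched registry controls would run at 45–50%. With the 35% that Section 11 quotes, the same calculation gives 27% and 11%.
- *That ARF-002 followed by SCD-003 demonstrates the bias.* The SCD-003 difference is 39.1 − 35.6 = 3.5 points, with an approximate 95% CI of −13 to +20. The sponsor offers another explanation for its results, ionized calcium control. The contrast does not isolate time.
- *That the registry analysis rests on the statement that mortality has not improved.* That sentence is disease background and is never used to justify comparability.
- *That the DSMB would overlook excess deaths.* Section 10 sets no mortality benchmark; the AKI literature is one of four review areas.

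**Conclusion.** The point holds as a gap in the analysis plan. The comparison has no matching, adjustment or sensitivity analysis for calendar period, so followed as written it could not separate an SCD effect from an era or selection difference. The documents do not show that such a difference exists, or how large it is.

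The size given here is conditional: a fixed 35% benchmark from a registry subgroup, an inert device, and drift of 0 to 9.4 points that is assumed rather than measured. Under those assumptions, drift raises the chance of an apparent benefit of 10 points or more from 29% to between 45% and 61% at n=16, and from 12% to between 28% and 48% at n=30. This should be fixed before the efficacy evaluation; it does not undermine the collection of safety data.

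**What to change.** In Section 11:

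1. Report the treatment years of the registry patients used as controls.
2. Report the matched risk difference with a 95% confidence interval, as an estimate.
3. Add a tipping-point analysis that lowers registry mortality over a range stated openly as an assumption, for example 0 to 15 points, and shows where any apparent benefit disappears. With 4 deaths in 16 (25%) against 35%, for instance, the benefit is gone at a shift of 35 − 25 = 10 points. The range should not be presented as estimated from SCD-003.
4. State in advance that a benefit that disappears within that range will be reported as not distinguishable from an era or selection difference.
5. Reconcile the sentences that describe the study as testing a hypothesis with the sentence that says it was not designed to judge efficacy.

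The cost is one extra analysis, the registry treatment years, and some wording. No further data on trial patients are needed. The price is a more cautious efficacy statement.

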3.2 STUDY ENDPOINT

In this Pilot study four (4) domains of interest have been designated. The four (4) domains are:

1. Patient Safety: Safety Endpoint Measures include adverse events, laboratory safety parameters, vital signs, EKG, ventilation status and hemodynamic variables.
2. Clinical Efficacy: The Primary Clinical Efficacy Endpoint Measure is in-hospital; 28 and 60-day all-cause mortality. Time to renal recovery and necessity for chronic dialysis up to day 60 will also be

determined. Additional efficacy endpoints include time to intensive care unit (ICU) discharge, and time to hospital discharge.

3. Device Integrity and Performance: The Endpoint Measure is SCD use without failure. This measure will help assess the integrity and performance of the SCD device.
4. SCD Mode of Action: Exploratory Endpoint Measures will include inflammatory cytokines, cell activation parameters and biomarkers at clinical sites with this capability.

Endpoints are defined in **Appendix D**.

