9. SAFETY

9.1. ADVERSE EVENTS

An Adverse Event is any sign, symptom, illness, clinically significant abnormal laboratory value or other adverse medical event that appears for the first time or worsens in a subject (control or treatment arm) during this clinical study, regardless of whether or not it is considered related to the device.

- Blood and lymphatic system disorders (e.g., anemia, disseminated intravascular coagulation (DIC), heparin-induced thrombocytopenia (HIT), hypercoagulation, leukocytosis, thrombocytopenia, and thrombocytosis);
- Cardiac disorders (e.g., atrial fibrillation, atrial flutter, bradycardia, cardiogenic shock, non-ST segment elevation myocardial infarction, sinus tachycardia, ventricular fibrillation, and ventricular tachycardia);
- Gastrointestinal disorders (i.e., blood in stool, constipation, distended abdomen, gastrointestinal bleeding, ileus, nausea, pancreatitis, vomiting)
- General disorders and administration site conditions (i.e., chest pain, generalized aching, high temperature, hypothermia, multi-organ failure)
- Infections and infestations (i.e., candidiasis, gangrene, klebsiella pneumonia infection, methicillin-resistant staphylococcus aureus (MRSA) infection, pneumonia, sepsis, septic shock, and urinary tract infection (UTI));
- Injury, poisoning and procedural complications (e.g., post procedural pain);
- Metabolism and nutrition disorders (i.e., hypercalcemia, hyperglycemia, hyperkalemia, hypernatremia, hypervolemia, hypocalcemia, hypoglycemia, hypokalemia, hypomagnesemia, hyponatremia, hypophosphatemia, malnutrition, metabolic acidosis, and metabolic alkalosis);
- Musculoskeletal and connective tissue disorders (e.g., muscle spasm);
- Nervous System Disorders (e.g., encephalopathy, mental deterioration, stroke);
- Psychiatric disorders (e.g., agitation, anxiety, confusion, insomnia, mental status changes);
- Renal and urinary disorders (e.g., acute retention of urine, renal failure);
- Respiratory, thoracic and mediastinal disorders (e.g., acute respiratory failure, aspiration pneumonia, atelectasis, hypoxemia, pleural effusion, pneumothorax, pulmonary thromboembolism, respiratory failure, and thoracic hemorrhage);
- Skin and subcutaneous tissue disorders (e.g., macular rash, skin ulcer); and
- Vascular disorders (e.g., deep vein thrombosis, hypertension, hypotension, and jugular vein thrombosis).

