9.2. SERIOUS ADVERSE EVENTS

Any Adverse Event, whether considered study-treatment related or not, which fits any of the criteria below, is considered a serious adverse event (SAE):

- Results in death
- Is life-threatening (meaning that the patient was at risk of death at the time of the event; this does not refer to an event which might have caused death if it had occurred in a more severe form)
- Requires in-patient hospitalization or prolongs the existing hospitalization
- Is a persistent disability/incapacity
- Is a congenital anomaly or birth defect
- Is considered an important medical event by the Principal Investigator (e.g., surgery, return to ICU, emergency procedures)

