9.4. ANTICIPATED ADVERSE EVENT

Co-morbidities and symptoms/laboratory/physiological deviations normally associated with pre-existing conditions (e.g., diabetes, ASHD, other C-V conditions, pneumonia, dialysis shunt problems, neurologic deficits) are considered “anticipated adverse reactions.” The investigator is required to take special care in differentiating concomitant illness events from those related to the therapy by use of patient history, relationship to treatment time and cartridge integrity, and other characteristics of clinical circumstances present at the time of the adverse experience, including drug interactions of concomitant medications and effects of surgical and/or medical procedures.

Adverse events associated with CRRT or underlying critical illness are also to be considered “anticipated”. Such events include, but are not limited to: thrombocytopenia, hyponatremia, hypokalemia, hypo- or hypercalcemia, hypo- or hyperglycemia, air embolism, hypotension, hemolysis, increased oxygenation requirements, leukopenia, arrhythmias, hypothermia, lactic acidosis, temporary decrease in cardiac output or cardiac index, disruption of skin integrity, bleeding, shock, bacteremia, hypotension, seizure, and death.

In addition, the following adverse events were experienced in the SCD-003 clinical trial and are considered anticipated:

- Blood and lymphatic system disorders (i.e., Anemia, Disseminated intravascular coagulation (DIC), Heparin-induced thrombocytopenia (HIT), Hypercoagulation, Leukocytosis, Thrombocytopenia, Thrombocytosis)
- Cardiac disorders (i.e., Atrial fibrillation, Atrial flutter, Bradycardia, Cardiogenic shock, Non ST segment elevation myocardial infarction, Sinus tachycardia, Ventricular fibrillation, Ventricular tachycardia)
- Gastrointestinal disorders (i.e., Blood in stool, Constipation, Distended abdomen, Gastrointestinal bleeding, Ileus, Nausea, Pancreatitis, Vomiting)
- General disorders and administration site conditions (i.e., Chest pain, Generalized aching, High temperature, Hypothermia, Multi organ failure)
- Infections and infestations (i.e., Candidiasis, Gangrene, Infection Klebsiella pneumonia, Infection MRSA, Pneumonia, Sepsis, Septic shock, UTI)
- Injury, poisoning and procedural complications (i.e., Post procedural pain)

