9.7.1. SCREENING PERIOD

Only adverse events, serious and not serious, directly related to the screening procedures will be captured during this period. Unrelated clinical adverse events that occur prior to enrollment will be considered part of the medical history.

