9.7.2. ENROLLMENT PERIOD THROUGH END OF STUDY

All adverse events that occur from the time of enrollment will be recorded as follows:

- Serious Adverse Events (identified in **Section 9.2**) will be recorded until Day 60 after enrollment, death, or patient withdrawal of study consent, whichever occurs first.
- Non-serious adverse events will be recorded until end of study follow-up period after enrollment, death, patient withdrawal of study consent or until hospital discharge, whichever occurs first.

Any serious adverse event (regardless of relationship to the treatment) occurring from the time of enrollment through end of study must be reported to CytoPherx Inc, or designee, within 24 hours of knowledge of the event.

Each clinical trial site will be supplied with written SAE reporting

instructions, SAE reporting forms and contact information for reporting of serious adverse events.

For any AE that is ongoing at the time of the initial report, periodic follow-up information will be required until the adverse event is resolved or the patient is no longer in the study, whichever occurs first.

The Investigator is responsible for all adverse events reporting to the Institutional Review Board (IRB) according to the requirements of the IRB and for providing clinical trial monitors with all medical records needed to source-verify the adverse events.

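### Section 11 matches or controls the registry comparison on adverse events and total treatment duration, neither of which is fixed when treatment starts and both of which may be consequences of it

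*Combined protocol and SAP*

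**What the plan says.** The Evaluation Plan in the synopsis and Section 10 provide for a comparison of mortality and dialysis dependency with historical controls. Section 11 names the source of the controls and says the comparison "will utilize the ppCRRT Registry to match for: etiology of AKI, co-morbidities, CRRT modality, dose and form of anticoagulant, adverse events". The next part of Section 11 uses the registry as a control for a list of CRRT treatment factors that begins "patient age, gender, primary cause of AKI, total treatment duration, CRRT modality".

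Other sections settle what these two items are:

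- Section 9.1: an adverse event is one that "appears for the first time or worsens in a subject (control or treatment arm) during this clinical study".
- Section 9.7.1: "Unrelated clinical adverse events that occur prior to enrollment will be considered part of the medical history". Only events caused by screening procedures are captured earlier.
- Section 9.7.2: adverse events are collected from enrolment, and serious ones "will be recorded until Day 60 after enrollment, death, or patient withdrawal of study consent, whichever occurs first".
- Section 3.2: "Safety Endpoint Measures include adverse events".
- Section 9.2: the first criterion for a serious adverse event is that it "Results in death".
- Synopsis, Evaluation Plan: time on CRRT is an additional endpoint.
- Appendix D: duration of renal support is a defined endpoint, censored at death or at Day 60 if the patient is still dependent.
- Section 11, opening: the device may shorten maintenance dialysis.

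**The concern.** Matching is meant to make the registry patients resemble the treated patients as they were before the device was applied. A variable that the device can change does not serve that purpose. If the device prevents a complication that leads to death, then choosing controls with the same complications as the treated patients removes that benefit from the comparison. If the device causes a complication, the same step removes the harm. Time on treatment raises the same problem, because it ends through recovery or death.

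The study's primary objective is safety, and Section 11 says the results will inform the design of a pivotal study. A comparison that can mask harm, or misstate benefit, is a poor basis for either.

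**Working it through.** The plan gives no effect size, matching algorithm or expected bias for this comparison, so there is no figure of its own to reproduce. The check is first textual. Illustrations under stated assumptions then show what can happen.

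**1. Can adverse events be read as a baseline factor?** Sections 9.1, 9.7.1 and 9.7.2 together place them in the study, from enrolment onward, with screening-procedure events as the only exception. Earlier unrelated events are medical history. Co-morbidities are a separate item in the same matching list, so adverse events cannot stand for them. No passage limits the item to events before CRRT or SCD.

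**2. Can total treatment duration be read as a baseline factor?** Up to 12 hours of CRRT may come before the observation period (Section 6.4), but the total is known only at the end. Several neighbouring items in the same list are tied to a time at or before CRRT initiation: urine output, fluid overload, vasoactive medication number and mean airway pressure. Duration is not.

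**3. What can matching on an adverse event do?** Take one complication that is sometimes followed by death. Assumed inputs: risk of the complication 50% in controls; mortality 60% with it and 10% without it; the device acts only through it.

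- Control mortality: 0.50 × 0.60 + 0.50 × 0.10 = 35%. This equals 100% − 65%, the registry survival that Section 11 cites for 1 to 7 days of CRRT.
- Device lowers the risk to 20%: 0.20 × 0.60 + 0.80 × 0.10 = 20%. True difference 20 − 35 = −15 points. Controls matched to the same 20% also have 20% mortality, so the matched difference is 0.
- Device raises the risk to 80%: 0.80 × 0.60 + 0.20 × 0.10 = 50%. True difference +15 points; matched difference again 0.
- If only a share of a −15 point effect passes through the complication, the matched difference is −15 × (1 − share): −11.25, −7.5 and −3.75 points for shares of 25%, 50% and 75%.

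**4. What can matching on duration do?** With constant hazards of death (d) and recovery (r), the chance that treatment ended in death is d/(d + r) at every duration. With d = 0.05 and r = 0.093 per day it is 0.05/0.143 = 35%. Matching on duration then shifts nothing. Adding unmeasured severity to that model shifted the mortality difference by about 1 point or less, in either direction.

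Larger shifts need hazards that change over time. One assumed shape:

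- death hazard 0.06 per day to day 7, then 0.02;
- recovery hazard to day 7 one quarter of its later value, set to give 35% control mortality by day 60;
- death hazard multiplied by exp(0.5 × S), with S standard normal and matched;
- both groups with at least 72 hours on treatment.

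| Assumed device effect | Difference without duration matching | With it |
|---|---|---|
| Death hazard halved, days 0–7 | −8.5 | −4.5 |
| Death hazard × 1.5, days 0–7 | +7.2 | +4.0 |
| Recovery × 1.5 | −3.0 | −5.6 |
| None | 0 | 0 |

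Benefit and harm can shrink, and benefit can be exaggerated. This is the steepest of five day-7 shapes tried at 35% mortality. For scale, one death is 1/16 = 6.25 points among the 16 patients of Section 10, or 1/30 = 3.3 among the 30 of Section 5.1.

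Whatever the hazards, exact matching on duration forces any comparison of duration itself to show no difference.

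**The case against.** **The wording is loose.** Where Section 11 goes on to explain the matching, it names the reason for CRRT, co-morbidities, modality, anticoagulant, age, size and PRISM II score; adverse events do not come back. The duration list speaks of the registry as a control, which may mean only that it supplies comparison data. With a safety objective set against historical data (Section 3.1), adverse events may be an item to compare that slipped into a list of items to match. This is fair, and it is why a change of wording is enough. But the text does say match, and nothing in the documents limits either item to values before treatment.

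**The comparison is exploratory.** Section 11 says the trial is not powered and not designed to assess efficacy, and no decision rule depends on the result. This stands and limits the consequence. Lack of power does not make conditioning on consequences of treatment harmless.

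**Duration is not, by name, an endpoint.** Correct. Total treatment duration is undefined, and its link to time on CRRT and duration of renal support is an inference, though a close one.

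**A stronger reading a reader might infer** is that, since adverse events include deaths, matching on them is matching on the outcome. The documents do not support that. In the adult US pilot (Section 2.4), 33 of 35 subjects had any adverse event, 23 of 35 a serious one and 11 of 35 one with outcome death. Matching on any event would have conditioned on almost nothing there. The mortality difference is zero by construction only if the fatal event itself is the matched variable, and no passage says so.

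**Conclusion.** The point holds as a matter of text and design: as written, the registry comparison conditions on two variables that treatment may change. The case is stronger for adverse events, whose timing and endpoint status the protocol defines. For duration it rests on overlap with two endpoints and on the protocol's own hypothesis that the device shortens dialysis.

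No size or direction of bias follows from the documents. The illustrations run from no shift to loss of an entire 15-point mortality difference for adverse events. For duration they run from no shift to about 4 points in the shape shown. All of these rest on assumed effects, hazards and exact matching, and none should be quoted as an estimate for this trial. A reader might also infer that the comparison must be biased against the device, or in its favour; neither is supported.

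The text should be corrected before the comparison is run. The point does not threaten the conduct of the study.

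**What to change.** In Section 11:

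1. Delete adverse events from the matching list and total treatment duration from the control list. Report both as outcomes.
2. State that matching or adjustment uses only variables fixed at or before CRRT/SCD start: age, size, PRISM II score, cause of AKI, co-morbidities, baseline eGFR, prior urine output and fluid overload, with modality, clearance and anticoagulation as prescribed at initiation.
3. Compare all treated patients with all matched controls.
4. If the set with at least 72 hours of SCD treatment is also reported, label it separately as selected on exposure. Apply the same time-on-CRRT restriction to the controls, counted from CRRT start, as an eligibility condition and not as a matching variable. This is needed because dropping duration removes the only item that gave controls a comparable time on CRRT.
5. If the duration list means only that the registry supplies comparison data, say so.

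The cost is a few lines of text and a little more analysis work, with no new procedure and no change in sample size.
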